28 JUN 2022

Version 5.0

Page: 9 of 149

	
Recruitment in the Essure arm is planned to continue as long as Essure is being implanted.
 
Enrollment in the laparoscopic tubal sterilization arm will be ceased once its enrollment reaches approximately 2:1 ratio laparoscopic tubal sterilization : Essure (anticipated).

Main variable(s)	
Section modified by Amendment 2 (Modification 7).
 
Pain: The proportion of subjects reporting AEs of chronic lower abdominal and / or pelvic pain after insertion of Essure System (ESS305) compared to the proportion of subjects reporting AEs of chronic lower abdominal and / or pelvic pain after laparoscopic tubal sterilization. Total incidence of pain events will be based on AE reporting.
 
Bleeding: The proportion of subjects reporting AEs of abnormal uterine bleeding after insertion of Essure System compared to the proportion of subjects reporting AEs of abnormal uterine bleeding after laparoscopic tubal sterilization. Total incidence of new onset or worsening abnormal bleeding events will be based on AE reporting.
 
Hypersensitivity / allergy: The proportion of subjects with adjudicated new onset or worsening allergic / hypersensitivity reactions (e.g., urticaria, rash, itching, as well as other symptoms that may be related to inflammation) in subjects wearing Essure inserts and in subjects undergoing laparoscopic tubal sterilization.
 
Autoimmune disorder: The proportion of subjects with adjudicated newly diagnosed or worsening autoimmune disorders in subjects wearing Essure inserts and in subjects undergoing laparoscopic tubal sterilization.
 
Proportion of subjects undergoing invasive gynecologic surgery after Essure placement (excluding second placement attempts); including Essure insert removal compared to the proportion of subjects undergoing invasive gynecologic surgery after laparoscopic tubal sterilization.

Time point / frame of measurement for primary variable(s)	
Section modified by Amendment 2 (Modification 17).
 
The main endpoints will be evaluated through 60 months of follow up after the procedure.

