- To identify the proportion of subjects who experience new onset or worsening allergic, hypersensitivity, or autoimmune-like reactions after Essure placement or laparoscopic tubal sterilization, and to better characterize these reported outcomes and any characteristics that may be related to their occurrence.
- To collect data on patient reported outcomes in subjects who have undergone hysteroscopic or laparoscopic tubal sterilization procedures.
- To collect rates of adverse events (AEs) in subjects undergoing Essure placement or laparoscopic tubal sterilization.

5. Study design

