- **Hypersensitivity / allergy:** The proportion of subjects with adjudicated new onset or worsening allergic / hypersensitivity reactions (e.g., urticaria, rash, itching, as well as other symptoms that may be related to inflammation). For potential allergic / hypersensitivity reactions, investigators will be instructed that an evaluation per standard medical practice must be performed in any subject presenting with urticaria, angioedema, unexplained rash, or unexplained itching. Evaluation will also be performed in subjects who present with other symptoms that could possibly be related to an inflammatory reaction (e.g., hair loss, fatigue, muscle pain, joint pain). Supplemental PRO Questionnaires will be used in both groups to actively solicit for such events. In addition, this evaluation will include collection and submission of blood and serum or plasma samples to a central laboratory for a nickel lymphocyte proliferation test (NiLPT), which is a measure of sensitization to nickel, a chromium lymphocyte proliferation test (LPT), which is a measure of sensitization to chromium, serum or plasma nickel level, serum or plasma titanium level, and inflammatory cytokines panel.

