In addition, any subject presenting with an AE of pelvic / lower abdominal pain and any subject presenting with symptoms she believes are due to hypersensitivity or allergic reaction will be evaluated per standard medical practice. In addition, this evaluation will include collection and submission of blood and serum samples to a central laboratory for a NiLPT, which is a measure of sensitization to nickel; a chromium LPT, which is a measure of sensitization to chromium; serum or plasma nickel level; and serum or plasma titanium level. If removal of a device or any other surgery is performed, pathological evaluation and metallurgic studies (if applicable) will be included. After the evaluation of the subject is complete, regardless of investigator's assessment as to whether or not a hypersensitivity / allergic reaction has occurred, all information will be forwarded to the adjudication committee (see Section 14.3) in a blinded fashion. If pathology / metallurgic studies are provided to the adjudication committee, it may not be possible to blind the members as to which group the subject belongs. Information forwarded to the adjudication committee will include all laboratory work for the subject, including baseline, 12 month (if applicable), and unscheduled draws. The final determination of whether or not a hypersensitivity / allergic event has occurred will be made by this committee.

- **Autoimmune disorders:** The proportion of subjects with adjudicated newly diagnosed or worsening autoimmune disorders in subjects wearing Essure inserts and in subjects undergoing laparoscopic tubal sterilization. Any subject presenting with symptoms indicating a potential autoimmune disorder will be evaluated per standard medical practice. All efforts will be made to obtain records of any diagnostic workup conducted by outside physicians. Blood samples for NiLPT, chromium LPT, serum or plasma nickel level, and serum or plasma titanium level will also be collected by the study site. An appropriate human leukocyte antigen (HLA) panel will be run on previously obtained baseline samples, if not already obtained at baseline. (The specific HLA type to be run will be dependent on the specific autoimmune disease the subject developed). If insufficient baseline sample exists, an additional sample may need to be drawn. After the evaluation of the subject is complete, regardless of investigator's assessment as to whether or not an autoimmune disorder exists, all

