10.3 Endpoints and planned statistical analyses

Section modified by Amendment 2 (Modification 3, Modification 25).

The following endpoints will be summarized as part of this study:

- The proportion of subjects reporting AEs of chronic lower abdominal and / or pelvic pain after insertion of Essure System compared to the proportion of subjects reporting AEs of chronic lower abdominal and / or pelvic pain after laparoscopic tubal sterilization. In both groups, AEs due to other apparent etiologies will be identified and excluded.
- The proportion of subjects reporting AEs of AUB after insertion of Essure System compared to the proportion of subjects reporting AEs of AUB after laparoscopic tubal sterilization. In both groups, AEs due to other apparent etiologies will be identified and excluded.
- Proportion of subjects with allergic / hypersensitivity reactions possibly attributed to wearing of Essure devices and allergic / hypersensitivity reactions in women undergoing laparoscopic tubal sterilization.
- Proportion of subjects with newly diagnosed autoimmune disorders in subjects wearing Essure inserts compared to subjects undergoing laparoscopic tubal sterilization.
- Proportion of subjects undergoing invasive gynecologic surgery after Essure placement (excluding second placement attempts), including Essure insert removal compared to the proportion of subjects undergoing gynecologic surgery after laparoscopic tubal sterilization.
- Patient reported outcome measures:
 - MOS SF-36 (Version 2);
 - PROMIS Scale V1.0—Pain Intensity 3a;
 - PROMIS Scale V1.0—Pain Interference 8a Participant Format;
 - AMSS and two intermenstrual bleeding questions used to characterize bleeding in subjects undergoing Essure placement and laparoscopic tubal sterilization;
 - FSQ: to investigate if scores on this instrument (continuous and categorical) correlate with chronic pelvic pain over the course of the study;
 - Supplemental PRO Questionnaires – a series of PRO tools used to actively solicit information on AEs commonly found in MDR reports with Essure;
 - Social Media Questionnaire – to elicit information about sources of influence on medical decisions, in particular, use of social media.

- Rates of AEs in subjects undergoing Essure placement and laparoscopic tubal sterilization;
- Characteristics of physicians performing the procedures;

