10.5 Planned interim analyses - amended

Section added by Amendment 2 (Modification 26) and Amendment 3 (Modification 1).

Section modified by Amendment 4 (Modification 2 and Modification 4)

Three interim analyses will be performed. The first will be initiated at the end of enrollment, the second will be initiated after all subjects complete 1 year of follow-up, and the third will be initiated at the point all subjects complete 3 years of follow-up. The purpose of these analyses is to formally review study data, at the request of FDA.

The following will be summarized as part of these interim analyses:

- Demographic information listed in Section 9.3.1.
- The proportion of subjects reporting AEs of chronic lower abdominal and / or pelvic pain after insertion of Essure System compared to the proportion of subjects reporting AEs of chronic lower abdominal and / or pelvic pain after laparoscopic tubal sterilization.
- The proportion of subjects reporting AEs of AUB after insertion of Essure System compared to the proportion of subjects reporting AEs of AUB after laparoscopic tubal sterilization.
- Proportion of subjects with allergic / hypersensitivity reactions possibly attributed to wearing of Essure devices and allergic / hypersensitivity reactions in women undergoing laparoscopic tubal sterilization.
- Proportion of subjects with newly diagnosed autoimmune disorders in subjects wearing Essure inserts compared to subjects undergoing laparoscopic tubal sterilization.
- Proportion of subjects undergoing invasive gynecologic surgery after Essure placement (excluding second placement attempts), including Essure insert removal compared to the proportion of subjects undergoing gynecologic surgery after laparoscopic tubal sterilization.
- Rates of AEs in subjects undergoing Essure placement and laparoscopic tubal sterilization.
- Device removals, and outcomes and resolutions, when associated with an AE.

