14.3 Adjudication Committee

Section modified by Amendment 2 (Modification 27).

An adjudication committee for allergy / hypersensitivity and immunology / autoimmune events will be formed. This will consist of a group of experts in allergy / immunology who are also experienced in evaluating immunological symptoms in subjects with medical devices. A gynecologist will be included. For possible hypersensitivity/allergic reactions, the committee will develop a list of Medical Dictionary for Regulatory Activities (MedDRA) terms that could represent hypersensitivity or allergy, irrespective of treatment group or investigator's assessment of relatedness. This list will be provided to investigators and will be stored in the ISF. All events with these terms will be sent to the committee for adjudication. In addition to the list of MedDRA terms, all subjects who are evaluated for pelvic pain will also be reviewed by the adjudication committee to assess whether or not an element of hypersensitivity could have played a role in the subject's pain. In the event that a subject reports that an AE is an allergic reaction, the AE will be investigated by the adjudication committee, regardless of whether the AE term is on the pre-established list.

For each case, the committee will receive:

- information from the eCRFs (blinded as to group assignment);
- baseline and supplemental study laboratory values;
- medical records (e.g. medical history or relevant medical information), consultant reports, other diagnostic studies (e.g. laboratory, radiological), and operative reports, as applicable, as well as any pathology reports.

In addition, all cases with a suspected or confirmed diagnosis of an autoimmune disease will be evaluated by the committee. The records listed above will be provided to the committee. In cases of suspected or confirmed autoimmune diseases, the adjudication committee may also request that previously collected baseline and/or one-year frozen serum be used to run additional tests. Results of HLA type will also be provided to the committee.

The committee will operate based on the allergy / immunology adjudication committee charter.

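### The hypersensitivity / allergy endpoint exists in two conflicting versions, and the version in the planned-analysis and interim lists puts an attribution condition on the Essure arm only

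*Protocol*

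**What the plan says.** Two sets of passages describe this endpoint, and they differ.

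**With an attribution condition on one arm.** The hypersensitivity item in Protocol 10.3 is the proportion of subjects with "allergic / hypersensitivity reactions possibly attributed to wearing of Essure devices and allergic / hypersensitivity reactions in women undergoing laparoscopic tubal sterilization". The item recurs in Protocol 10.5 ("Proportion of subjects with allergic / hypersensitivity reactions possibly attributed to wearing of Essure devices", followed by the same unrestricted laparoscopic half) and as item 4 of the list in SAP section 7. All three are current text, outside the amendment history.

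**With no attribution condition.**
- Protocol section 4 sets the objective as "new onset or worsening allergic, hypersensitivity, or autoimmune-like reactions after Essure placement or laparoscopic tubal sterilization".
- The Synopsis, under main variables, counts adjudicated reactions "in subjects wearing Essure inserts and in subjects undergoing laparoscopic tubal sterilization".
- Protocol 5.2.1 defines the endpoint as "The proportion of subjects with adjudicated new onset or worsening allergic / hypersensitivity reactions" and adds: "The final determination of whether or not a hypersensitivity / allergic event has occurred will be made by this committee".
- Protocol 14.3 has the committee draw up its list of terms for review "irrespective of treatment group or investigator's assessment of relatedness".
- SAP 6.2 brings validated outcomes into the analyses. SAP 6.4 bases the event on the committee's decision and takes as numerator the subjects with a treatment-emergent event. Neither has a separate rule by arm.
- SAP Table 2 lists the endpoint without attribution, but describes the reactions as reported where the Protocol has adjudicated.

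**The concern.** Relatedness is a legitimate thing to tabulate, but a relatedness filter on one arm only does not give a like-for-like comparison. Background reactions unrelated to either procedure occur in both groups. Under the list wording they can be removed from the Essure numerator but not from the laparoscopic one.

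The neighbouring items in Protocol 10.3 show that this is not the general pattern. The pain and bleeding items exclude events with another apparent cause, but in both groups. The autoimmune item has no attribution condition. Only the hypersensitivity item conditions one arm.

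This is one of five main endpoints in SAP Table 2, in a safety study required by the FDA. Two statisticians working from these documents could produce different Essure counts from the same data, and the difference would always run in one direction.

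**Working it through.** The plan gives no figure to reproduce: no event rate, no attribution share, no fixed sample size and no power calculation. The check is therefore a comparison of definitions, followed by an illustration on stated assumptions.

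**Step 1. Which version governs which analysis?**

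| Place | Condition on Essure | Condition on laparoscopic arm |
|---|---|---|
| Protocol section 4, Synopsis, 5.2.1 | none | none |
| SAP 6.2, 6.4, Table 2 | none | none |
| Protocol 10.3 (planned analyses) | possible attribution to the device | none |
| Protocol 10.5 (interims) | possible attribution to the device | none |
| SAP section 7, item 4 (interims) | possible attribution to the device | none |

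For the final analysis, Protocol 10.1 refers statistical matters to the SAP, and the SAP counting rules have no filter. For the interims the SAP does not settle the matter, because its own interim list carries the one-sided wording. The interim tables are where a literal reading is most likely.

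**Step 2. Could the filter be applied?** No passage defines possible attribution or names who judges it. A candidate variable exists, however. Protocol 9.6.1.2.6 has investigators record a yes/no causal assessment, and SAP 6.5.1 tabulates related events by procedure or device, including the Essure insert. A programmer following SAP section 7 would have something to filter on.

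**Step 3. Effect if it is applied.** Let p_E and p_L be the true proportions with an adjudicated reaction, and f the share of affected Essure subjects with a reaction judged attributable.

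- Counted Essure proportion = f × p_E; counted laparoscopic proportion = p_L.
- Apparent ratio = f × (p_E / p_L).
- Apparent difference = f × p_E − p_L.

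With equal true rates (p_E = p_L = p), the ratio is f and the difference is p × (f − 1). Both p and f are assumptions. At p = 5%:

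| f | Essure counted | Laparoscopic | Apparent ratio | Apparent difference (points) | True ratio that would appear as 1.0 (1/f) |
|---|---|---|---|---|---|
| 1.00 | 5.00% | 5% | 1.00 | 0 | 1.00 |
| 0.90 | 4.50% | 5% | 0.90 | −0.50 | 1.11 |
| 0.75 | 3.75% | 5% | 0.75 | −1.25 | 1.33 |
| 0.50 | 2.50% | 5% | 0.50 | −2.50 | 2.0 |
| 0.25 | 1.25% | 5% | 0.25 | −3.75 | 4.0 |

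The ratio does not depend on p; the difference does. At f = 0.50 it is −1.0, −2.5, −5.0 or −10.0 points for p = 2%, 5%, 10% or 20%.

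**Step 4. After the fix.** With one definition in both arms, f = 1. Equal true rates then give a ratio of 1.00 and a difference of 0 at any p.

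**The case against.** The best defence is that the three passages are summary lists, while the text that defines and counts the endpoint is symmetric. A team applying SAP 6.2 and 6.4 would use committee-validated events in both arms, and the final count would be unaffected. This stands for the final analysis. It does not clear the interims, where the SAP carries the conditioned wording itself.

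A second defence is that the study is exploratory and that Protocol 10.5 and SAP section 7 rule out statistical comparison at the interims. No error rate is at stake, which is correct. Proportions printed side by side by arm are still read as a comparison, and a definitional bias misleads without a p-value.

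Third, other tables would show an excess. SAP 6.5.1 reports all treatment-emergent events and events of special interest, and the latter include potential new or worsening allergy symptoms in both arms (Protocol 9.6.1.1). SAP 6.2 also tabulates the original assessments against the adjudicated result. This limits the harm but leaves the main endpoint table ambiguous.

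Some stronger readings are tempting, and the documents do not support them:
- *The filter undoes blinded adjudication.* The committee decides only whether an event occurred. Relatedness is a separate investigator judgement, and a filter applied afterwards does not unblind the committee.
- *A seasonal or drug rash is automatically a laparoscopic-arm case.* Protocol 5.2.1 asks for evaluation of unexplained rash or itching, and whether an event counts depends on the committee.
- *The 3-year interim results are certain to be published with this bias.* Protocol section 11 says that the FDA may post them and that the content is to be agreed with the sponsor.

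**Conclusion.** The concern holds as an internal contradiction in a main endpoint, with its greatest force for the three interim analyses. A reader might infer from Protocol 10.3 alone that the endpoint favours Essure by definition, the final analysis included. The documents do not support that, because the passages that define the endpoint and the SAP rules that count it have no attribution condition in either arm.

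The direction is certain if the lists are followed: any f below 1 lowers the Essure proportion only. The size is unknown. The ratios in the working rest wholly on assumed values of f, and the differences also on assumed event rates. Because the condition asks only for possible attribution, f could be close to 1 and the effect small. Under the SAP 6.2 and 6.4 rules it is zero.

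**What to change.** 1. In Protocol 10.3, Protocol 10.5 and SAP section 7 item 4, delete the words limiting Essure reactions to those possibly attributed to the device.
2. In all three, use the Protocol 5.2.1 event in both arms ("The proportion of subjects with adjudicated new onset or worsening allergic / hypersensitivity reactions"), regardless of relatedness.
3. In SAP Table 2, change reported to adjudicated, so that the table agrees with the rule stated in SAP 6.4.
4. If attribution to the device is of interest, show it in a separate descriptive table for the Essure arm, and state who makes the judgement and on what scale.
5. If any interim table has already been produced, record which version of the endpoint it used.

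The cost is wording in two protocol sections and two places in the SAP. No new data are needed. The Essure count may be higher than under the conditioned wording.

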10.4 Determination of sample size

Section modified by Amendment 2 (Modification 6).

Overall enrollment will be dependent on availability of Essure.

Recruitment in the Essure arm is planned to continue as long as Essure is being implanted.

Enrollment in the laparoscopic tubal sterilization arm will be ceased once its enrollment reaches approximately 2:1 ratio laparoscopic tubal sterilization : Essure (anticipated).

10.5 Planned interim analyses - amended

Section added by Amendment 2 (Modification 26) and Amendment 3 (Modification 1).

Section modified by Amendment 4 (Modification 2 and Modification 4)

Three interim analyses will be performed. The first will be initiated at the end of enrollment, the second will be initiated after all subjects complete 1 year of follow-up, and the third will be initiated at the point all subjects complete 3 years of follow-up. The purpose of these analyses is to formally review study data, at the request of FDA.

The following will be summarized as part of these interim analyses:

- Demographic information listed in Section 9.3.1.
- The proportion of subjects reporting AEs of chronic lower abdominal and / or pelvic pain after insertion of Essure System compared to the proportion of subjects reporting AEs of chronic lower abdominal and / or pelvic pain after laparoscopic tubal sterilization.
- The proportion of subjects reporting AEs of AUB after insertion of Essure System compared to the proportion of subjects reporting AEs of AUB after laparoscopic tubal sterilization.
- Proportion of subjects with allergic / hypersensitivity reactions possibly attributed to wearing of Essure devices and allergic / hypersensitivity reactions in women undergoing laparoscopic tubal sterilization.
- Proportion of subjects with newly diagnosed autoimmune disorders in subjects wearing Essure inserts compared to subjects undergoing laparoscopic tubal sterilization.
- Proportion of subjects undergoing invasive gynecologic surgery after Essure placement (excluding second placement attempts), including Essure insert removal compared to the proportion of subjects undergoing gynecologic surgery after laparoscopic tubal sterilization.
- Rates of AEs in subjects undergoing Essure placement and laparoscopic tubal sterilization.
- Device removals, and outcomes and resolutions, when associated with an AE.

The PS model will be developed, after all subjects have been enrolled, by an outcome-blinded independent party which will only have access to baseline characteristics and sterilization group. Balance of the PS baseline characteristics will be assessed at the 3-year interim analysis and end of study; if necessary, the process will be reevaluated to ensure balance of baseline characteristics throughout the study. The first interim analysis will be initiated after the PS matching process has completed. All 3 interim analyses will be performed on a PS-matched population in order to adjust for measured confounding as well as on the total population. In other words, the main analysis sets are the Adjusted Full Analysis Set (PS-matched population among subjects where a sterilization procedure of choice was

attempted) and the Full Analysis Set (sterilization procedure of choice was attempted) for the interim analyses. A Reliance Set will consider women relying on the sterilization method selected at the index event.

For all the outcomes and variables, a descriptive analysis will be performed and no statistical comparison will be made. For continuous data, N, mean, standard deviation, min, and max will be provided and for categorical data, frequency and percentages will be provided. Unless otherwise specified, the analyses will be presented in a way that events will be assigned to the treatment which was given initially at the index event.

Summaries for the interim analyses will use all data up to the data cutoff dates, which will be at the time enrollment ends, after all subjects complete 1 year of follow-up, and at the end of 3 years of follow-up. Serology data (cytokines, nickel and titanium levels, and nickel LPT results) will be summarized in the interim analysis to be performed at the end of 3 years of follow-up. The interim analysis report will also include a description of the pathologic and histologic findings of fallopian tubes, and individual dossiers provided to the Adjudication Committee in cases of potential hypersensitivity/allergy/autoimmune reactions.

Results of each interim analysis will be summarized in a separate report.

The interim analysis reports will be submitted no later than 3 months after database lock for each interim analysis data cutoff date.

11. Interim and final post market surveillance report

Section added by Amendment 2 (Modification 26). Section modified by Amendment 4 (Modification 1)

Bayer will submit an interim postmarket surveillance report every 6 months for the first 2 years of the postmarket surveillance and annually thereafter from the date of approval of the 522 postmarket surveillance study plan which was anticipated to be 04 SEP 2016.

Per FDA's final guidance document on Postmarket Surveillance issued on 16 MAY 2016 (located at

<http://www.fda.gov/downloads/MedicalDevices/DeviceRegulationandGuidance/GuidanceDocuments/ucm268141.pdf>), after approval of the study plan, FDA may post surveillance plan parameters related to the study design and objectives on the FDA postmarket surveillance webpage (<http://www.accessdata.fda.gov/scripts/cdrh/cfdocs/cfPMA/pss.cfm>). Furthermore, the FDA may post the following information from interim postmarket surveillance reports in the following conditions:

- Number of study sites enrolled (to be updated after submission of each interim report);
- Number of subjects enrolled (to be updated after submission of each interim report);
- Interim summary data and / or analyses thereof when appropriate to protect the public health, e.g., when interim results raise safety concerns or may otherwise impact treatment. In the event that posting the interim results is appropriate to protect the public health, the public release of data will be coordinated between Bayer and FDA.

- Interim summary data and / or analyses thereof, to be performed at the end of 3 years of follow-up. The interim data for public release will be agreed to between Bayer and FDA.

The final report will be submitted no later than 3 months after postmarket surveillance study completion (as defined by database lock).

12. Data handling and quality assurance

